7.2 SAFETY AND OTHER ASSESSMENTS

The following procedures/evaluations will be performed for safety assessments:

- **Screening visit** – Review of medical history, physical examination (including rectal examination) following consent, vital signs [ie, temperature, pulse, and blood pressure], height and weight
- **Assess adherence to intervention. Inquire about adverse events with phone calls during the fitting and treatment periods.**
- **Review medical records** prior to and during study participation for adverse events. This process will adhere to Health Insurance Portability and Accountability Act (HIPAA) rules, other relevant federal or state laws, and local institutional requirements should be followed, as applicable.
- **Administer questionnaires and a daily diary to record subject-reported outcomes**
- **Assessment of adverse events.** Adverse events will be evaluated promptly. Subjects will be referred for additional tests and/or provided treatment.

7.3 ADVERSE EVENTS AND SERIOUS ADVERSE EVENTS

7.3.1 DEFINITION OF ADVERSE EVENTS (AE)

Utilizing ISO 14155:2011, an adverse event (AE) is any untoward medical occurrence, unintended disease or injury, or untoward clinical signs (including abnormal laboratory findings) in subjects, users or other persons, whether or not related to the investigational medical device. An adverse event (also referred to as an adverse experience) can be associated with the use of a device, without any judgment about causality.

NOTE 1 This definition includes events related to the investigational medical device or the comparator, if applicable.

NOTE 2 This definition includes events related to the procedures involved.

NOTE 3 For users or other persons, this definition is restricted to events related to investigational medical devices.

7.3.2 DEFINITION OF SERIOUS ADVERSE EVENTS (SAE)

Adverse event that:

- a) Led to death,

b) Led to serious deterioration in the health of the subject, that either resulted in

- 1) a life-threatening illness or injury, or
- 2) a permanent impairment of a body structure or a body function, or
- 3) in-patient or prolonged hospitalization, or
- 4) medical or surgical intervention to prevent life-threatening illness or injury or permanent impairment to a body structure or a body function,

c) Led to fetal distress, fetal death or a congenital abnormality or birth defect

NOTE Planned hospitalization for a pre-existing condition, or a procedure required by the CIP, without serious deterioration in health, is not considered a serious adverse event.

7.3.3 CLASSIFICATION OF AN ADVERSE EVENT

7.3.3.1 SEVERITY OF EVENT

AEs will be graded according to the severity of the AE and ranges from Grade 1 (mild AE), Grade 2 (moderate AE), Grade 3 (severe AE) and Grade 4 (life-threatening or disabling AE) to Grade 5 (death related to AE).

Adverse events will be graded as follows:

- Mild: discomfort noticed but no disruption of normal daily activity.
- Moderate: discomfort sufficient to reduce or affect daily activity.
- Severe: inability to work or perform normal daily activity.
- Life threatening: represents an immediate threat to life.

Relationship to study device and/or procedure will be determined by the Investigator according to the following criteria.

- None: No relationship between the event and the administration of study device. The event is related to other etiologies, such as concomitant medications or subject's clinical state.
- Unlikely: The current state of knowledge indicates that a relationship to study device is unlikely or the temporal relationship is such that study device would not have had any reasonable association with the observed event.
- Possible: A reaction that follows a plausible temporal sequence from administration of the study device and follows a known response pattern to the suspected study device. The reaction might have been produced by the subject's clinical state or other modes of therapy administered to the subject.

- Probable: A reaction that follows a plausible temporal sequence from administration of the study device and follows a known response pattern to the suspected study device. The reaction cannot be reasonably explained by the known characteristics of the subject's clinical state or other modes of therapy administered to the subject.

7.3.3.2 RELATIONSHIP TO STUDY INTERVENTION

For the purpose of safety analyses, all AEs that are classified as unlikely, possible, or probable will be considered treatment-related events.

7.3.3.3 ANTICIPATED ADVERSE EVENTS

Anticipated risks for this study include:

- Mild discomfort
- Unexpected expulsion of the device
- New onset, or, if pre-existing, increased anorectal pain or discomfort
- Diarrhea
- Abdominal pain
- Anorectal irritation, pain, soreness
- Rectal, anal, or perianal infection
- Device over-insertion or device migration into anal canal or rectum
- Injury to anus, anal canal, or rectum
- New onset, or, if pre-existing, increased anorectal urge
- New onset, or, if pre-existing, increased abdominal gas
- New onset, or, if pre-existing, increased hemorrhoids or rectal bleeding
- New onset, or, if pre-existing, increased colonic obstruction or fecal impaction
- Perforation of anal canal or rectum
- Device breakage
- Discomfort, bruising, redness, swelling, bleeding around the site of the blood draw
- Feeling of lightheadedness when blood is drawn
- Infection at the site of the blood draw
- Rectal bleeding due to rectal catheter use

There may be additional risks to subjects or embryos or fetuses in women who are of childbearing potential that are not known at this time.

7.3.4 TIME PERIOD AND FREQUENCY FOR EVENT ASSESSMENT AND FOLLOW-UP

Adverse events will be recorded from Screening through study exit. Adverse events should be assessed and reported to the sponsor from enrolment through resolution or study exit, whichever comes first. Subjects should continue to be followed per standard of care after study exit.

7.3.5 ADVERSE EVENT REPORTING

Each subject must be carefully monitored for the development of any adverse events. This information should be obtained in the form of non-leading questions (e.g., "How are you feeling?") and from signs and symptoms detected during each examination, observations of study personnel, and spontaneous reports from subjects.

All adverse events (serious and non-serious) spontaneously reported by the subject and/or in response to an open question from study personnel or revealed by observation, physical examination or other diagnostic procedures will be recorded in the source documentation and on the appropriate page of the CRF. Any clinically relevant deterioration in laboratory assessments or other clinical findings is considered an adverse event and must be recorded on the appropriate pages of the CRF. When possible, signs and symptoms indicating a common underlying pathology should be noted as one comprehensive event. Participants who have a T score ≥ 70 on the PROMIS depression instrument will be managed according to the flow diagram immediately after Section 11, References.

7.3.6 REPORTING UNANTICIPATED PROBLEMS INVOLVING RISKS TO SUBJECTS OR OTHERS (UPIRTSOS)

Adverse Event reporting will follow the Mayo Clinic IRB policy for submitting reportable events. Consistent with this policy, "an UPIRTSO is defined as any problem or event which, in the opinion of the local Investigator, meets all reporting criteria for events that are serious, unanticipated and related (at least "possibly" related) to research procedures or the study device, as noted in protocol section 7.4.1.

The Principal Investigator must report internal UPIRTSOs to the IRB, using the IRB electronic Reportable Event form, **within five working days** of the PI or study team becoming aware of the problem or event. Reportable events having the potential to meet the UPIRTSO criteria will be forwarded to the IRB. An IRB Chairperson has the authority to determine that the criteria were not met. If the IRB Chairperson considers the event to be a UPIRTSO it must be reviewed by a convened IRB. The investigator is notified in writing. The review, determination, and relevant communication is documented in the IRB electronic system. A UPIRTSO, as determined by the convened IRB, is reported to the Mayo Clinic Institutional Official and relevant federal agencies, when required, within 30 days from the date of IRB determination. The investigator is notified in writing of this action.

The timing of investigator reporting of protocol violation/deviations to the IRB, using the IRB electronic Reportable Event form, is dependent on the severity of the protocol violation/deviation. Major protocol violations/deviations that affect the rights and welfare of subjects and others, increase risks to subjects and others, decrease potential benefits, compromise the integrity or validity of the

research; or represent willful or intentional misconduct must be reported by the investigator **within five working days** of the PI or study team becoming aware of the violation/deviation. Minor protocol violations and/or deviations should be summarized and submitted to the IRB at the time of continuing review.

Information that indicates a significant new serious risk or increased severity of known risk, or a safety issue which requires immediate action must be reported to the IRB using the IRB electronic Modification form, within **five working days** of the PI or study team becoming aware of the information. The modification must be titled **Urgent Action Required** and include the Subject Notification Form attachment. The investigator is responsible to review new information to determine if it meets the above criteria for immediate action.

If IRB reporting requirements change during the study, the most current IRB reporting policies will be followed.

All SAEs must be reported whether or not considered causally related to the study device. SAE forms will be completed and the information collected will include subject number, a narrative description of the event and an assessment by the Investigator as to the severity of the event and relatedness the to study device. Follow-up information on the SAE may be requested by Minnesota Medical Technologies or designee.

Contact Information:

[REDACTED]
Minnesota Medical Technologies
[name]
[name]

Fax:

[REDACTED]

Preferred method of contact is by email:

[REDACTED]

Follow-Up SAE Reports:

The Investigator must continue to follow the subject until the SAE has resolved or until the condition becomes chronic in nature, stabilizes (in the case of persistent impairment) or the subject dies.

Within 24 hours of receipt of follow-up information, the Investigator must update the SAE form for the study and submit any supporting documentation (e.g., subject discharge summary or autopsy reports) via fax or e-mail.

For both serious and non-serious adverse events, the Investigator must determine the severity, anticipatedness, and the relationship of the event to study device and/or study procedure.

7.3.7 REPORTING EVENTS TO PARTICIPANTS

Any information which could impact a subject's decision to participate in the study will be communicated to them in writing.

7.3.8 EVENTS OF SPECIAL INTEREST

Anoscopy will be performed for subjects who complain of new anorectal bleeding or moderate or severe pain on the bowel diary. After the treatment period, all individuals who withdraw for reasons other than personal preference (i.e., for medical reasons) and a minimum of 50% of all patients shall undergo an evaluation by anoscopy following the treatment period to assess for device related trauma

If signs of a major side effect (e.g., rectal perforation) should occur, the subject will be treated as clinically indicated and Principal Investigator and Sponsor will be notified immediately. Such events should be reported on the case report form. Unanticipated serious adverse events will be immediately reported to the sponsor.

A device deficiency is defined as inadequacy of a medical device with respect to its identity, quality, durability, reliability, safety or performance. Device deficiencies include malfunctions, use errors, and inadequate labelling.

A malfunction is defined as a failure of an investigational medical device to perform in accordance with its intended purpose when used in accordance with the instructions for use or clinical protocol.

If a device deficiency or device malfunction is noted, this will be immediately reported by the site to the sponsor.

7.3.9 REPORTING OF PREGNANCY

Reports of pregnancy should be communicated by the site to the study sponsor immediately.

7.4 UNANTICIPATED PROBLEMS

7.4.1 DEFINITION OF ANTICIPATED AND UNANTICIPATED ADVERSE EVENTS, UNANTICIPATED PROBLEM (UP)

Per ISO 14155:2011, an anticipated serious adverse device effect (ASADE) is an effect which by its nature, incidence, severity or outcome has been identified in the risk analysis report.

Per ISO 14155:2011, unanticipated serious adverse device effect (USADE) IS A serious adverse device effect which by its nature, incidence, severity or outcome has not been identified in the current version of the risk analysis report. Per 21 CFR 812, If there are serious, unexpected adverse reactions associated with the use of the study device, Minnesota Medical Technologies or designee will notify the appropriate regulatory agency(ies) and all participating investigators on an expedited basis. An unanticipated serious adverse device effect (USADE) is a serious adverse device effect which by its nature, incidence, severity or outcome has not been identified in the current version of the risk analysis report. It is the responsibility of the Investigator and sponsor to promptly notify the Institutional Review Board (IRB) of all unexpected serious adverse device reactions involving risk to human subjects. A sponsor who determines that an unanticipated adverse device effect presents an unreasonable risk to subjects shall terminate all investigations or parts of investigations presenting that risk as soon as possible. Termination shall occur not later than 5 working days after the sponsor makes this determination and not later than 15 working days after the sponsor first received notice of the effect. The sponsor shall report the results of such USADE evaluation to FDA and to all reviewing IRBs and participating investigators within 10 working days after the sponsor first receives notice of the effect. Thereafter the sponsor shall submit such additional reports concerning the effect as FDA requests.

In accordance with the Institutional Review Board (IRB) at Mayo Clinic, an unanticipated problem involving risk to subjects or others (UPIRTSO) will be defined any problem or event which, in the opinion of the Investigator meets all three of the following criteria:

- Serious: Problem or event that resulted in significant harm, (which may be physical, psychological, financial, social, economic, or legal) or place the subjects or others at a greater risk of harm than was previously known or recognized. Note that actual harm need not have occurred.
- Unanticipated: A problem or event that was unforeseeable at the time of its occurrence and meets one or more of the following criteria:
 - Not already described as a potential risk in the approved informed consent
 - Not already described as a potential risk in the approved protocol
 - Not listed in the Investigator's Brochure
 - Not part of an underlying disease
 - Occurred at an increased frequency or at an increased severity than expected.
- Related: A problem or event is "related" if it is possibly related to the research procedures.

7.4.2 UNANTICIPATED PROBLEM REPORTING

All UPIRTSOs will be reported to the study Sponsor and the Mayo Clinic IRB who will decide whether the event(s) should be reported to regulatory agencies (e.g., OHRP, FDA, etc).

7.4.3 REPORTING UNANTICIPATED PROBLEMS TO PARTICIPANTS

Subjects will be notified about any significant or new information which could impact their decision to participate in the study. This may include unanticipated problems.

8 STATISTICAL CONSIDERATIONS

8.1 STATISTICAL HYPOTHESES

The hypotheses for the primary endpoints, which all apply to subjects with FI, are indicated below. For the primary study, these endpoints will be assessed for all 60 participants and separately for the 10 mm and 13 mm devices (versus baseline).

- 1. Primary Effectiveness Endpoint: A Relative Percentage Change in Episodes of Accidental Bowel Leakage (ABL) Determined by Comparing Treatment Results to Pre-treatment Results From the Baseline Period as Measured by Daily Diary Recordings . [Time Frame: Reduction in accidental bowel leakage from Baseline (Weeks 1-4) through Treatment period (approximately Weeks 9-12).]**

Measure Type	Primary
Measure Title	Primary Effectiveness Endpoint: A Relative Percentage Change in Episodes of Accidental Bowel Leakage (ABL) Determined by Comparing Treatment Results to Pre-treatment Results From the Baseline Period as Measured by Daily Diary Recordings.
Measure Description	This primary effectiveness endpoint will be calculated as a relative percentage of the baseline Accidental Bowel Leakage (ABL) using the following equation: % reduction in ABL = 100*(baseline period ABL - treatment period ABL) / (baseline period ABL)
Time Frame	Reduction in accidental bowel leakage from Baseline (Weeks 1-4) through Treatment period (approximately Weeks 9-12).

Secondary Efficacy Endpoint(s):

- The mean % reduction in Fecal Incontinence Severity Index (FISS) score from the baseline period to the end of the treatment period, calculated according to the following equation: % reduction in FISS = 100% (baseline period FISS - end treatment period FISS) / (baseline period FISS).
- The proportion of subjects in whom the frequency of FI episodes during the treatment period is greater than or equal to 75% lower than the frequency observed during baseline period.
- The proportion of subjects in whom, during treatment period, the device will reduce the number of days with FI by 50% as compared to baseline.
- The proportion of subjects in whom the device will reduce the volume of FI during the treatment period as compared to baseline.
- The proportion of subjects in whom the Minnesota Medical Technologies Anal Insert Device reduces the proportion of FI episodes which are associated with diarrhea.
- The proportion of subjects in whom the Minnesota Medical Technologies Anal Insert Device reduces the number of episodes of passive and of urge FI
- The proportion of subjects in whom the Minnesota Medical Technologies Anal Insert Device I improves the Quality of Life (QOL) related to FI during the treatment period as compared to baseline.

- The proportion of subjects in whom the Minnesota Medical Technologies Anal Insert Device will affect the composition of stool leakage during the treatment period as compared to baseline.
- The proportion of subjects are satisfied with the Minnesota Medical Technologies Anal Insert Device.
- The time for which a bowel movement can be deferred after the occurrence of urgency will be affected by the Minnesota Medical Technologies Anal Insert Device.
- The proportion of complete bowel movements will be affected by the Minnesota Medical Technologies Anal Insert Device during the treatment period as compared to baseline.
- Treatment with the Minnesota Medical Technologies Anal Insert Device will affect anxiety and depression during the treatment period as compared to baseline.
- The Minnesota Medical Technologies Anal Insert Device reduces the use of medications for FI during the treatment period as compared to baseline.

- [REDACTED]
- [REDACTED]
- [REDACTED]

8.2 SAMPLE SIZE DETERMINATION

The sample size determination was based on literature review. In a controlled clinical trial with clonidine, the mean and standard deviation (SD) for weekly FI episodes over a 4 week baseline period was 2.642 and 1.066 respectively in the placebo group.²⁹

Assuming a mean frequency of 2.6 and a very conservative estimated SD of differences (post-pre treatment) of 1.3, a sample size of 13 subjects provides 90% power with a two sided paired t test and an alpha level of 0.05 to detect a 50% reduction (i.e., from 2.6 to 1.3 episodes/week) in the number of episodes of FI. Hence, a sample size of 30 FI subjects per group (i.e., 10mm and separately 13 mm inserts) is more than sufficient.

In order to test whether the treatment provides an improvement up to 60% response rate (50% response) from an assumed historical rate of 30%, the exact one-sample binomial test (2-sided) will be used at the 0.05 level. A sample size of n=30 provides 90% power to detect this effect.

No previous studies have evaluated [REDACTED]. We estimated that FI subjects [REDACTED] will [REDACTED] of the [REDACTED] (i.e., [REDACTED]). If [REDACTED] with a sample size of [REDACTED] in the [REDACTED] and [REDACTED] in the [REDACTED] (i.e., [REDACTED] devices), provides [REDACTED] [REDACTED].

For anoscopy, the sample size of 31 patients (i.e., 52%), provides 80% power to detect an event rate of 5% and 96% power to detect an event rate of 10%. In this context, an event refers to a side effect such as an anal fissure.

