- 1) Subjects who begin with the 10 mm device will use the device for a minimum of 2 weeks during the fitting period. Subjects will be asked to complete daily bowel diaries to determine the percent reduction in FI episodes, and subject comfort will be assessed using question #7 on the QUEST questionnaire. (a) If greater than or equal to 75% reduction in FI episodes is observed during this fitting period, the subject will proceed immediately to the treatment period and will continue using the 10mm device for the entire treatment period. (b) If the reduction in FI episodes is less than 75%, and the QUEST score is 1-2 (indicating dissatisfaction with comfort), the subject will proceed immediately to the treatment period and will continue using the 10mm device for the entire treatment period. (c) If the reduction in FI episodes is less than 75%, and the QUEST score is 3-5 (indicating satisfaction with comfort), the participant will use 13 mm devices for the remaining 2 weeks of their fitting period and complete daily bowel diaries.
- 2) At the end of this fitting period, the subject comfort will be reassessed with question #7 of the QUEST questionnaire. Subjects who report QUEST scores of 1-2 (indicating dissatisfaction with comfort) with the 13mm device will use the 10mm device for the entire treatment period. However, subjects who report QUEST scores of 3-5 (indicating satisfaction with comfort) at the end of the fitting period will proceed immediately to the treatment period and will continue using the size 13mm device for the entire treatment period.
- 3) Subjects who begin with the 13mm device will use the device for a minimum of two weeks during the fitting period. Thereafter, the subject will proceed to the treatment period and will continue using the 13mm device for the entire treatment period.

Subjects will be contacted at least twice per month during the fitting period. Attempts will be made to space these calls at an interval of 7 days.

This sequence is shown in the following flow diagram:

5. Subjects proceed to the 4-week treatment period, use the Minnesota Medical Technologies Anal Insert Devices, and record every bowel movement and episode of fecal incontinence in a daily diary for 4 weeks. Subjects will be asked to complete questionnaires on a weekly basis and also complete additional questionnaires once at the end of the treatment period. Subjects will be asked to mail bowel diaries and questionnaires to the study site every week.

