6.1.2 DEVICE ADMINISTRATION

The sizes to be evaluated in this study are:

- Minnesota Medical Technologies Anal Insert Device 10 mm size – to be inserted in the anorectum during the day. Subjects who have nocturnal FI should also use the device at night.
- Minnesota Medical Technologies Anal Insert Device 13 mm size – to be inserted in the anorectum during the day. Subjects who have nocturnal FI should also use the device at night.

At the screening visit, the 10 mm, and, if necessary thereafter, the 13 mm device will be inserted into the rectum to determine if the device stays in situ while subjects are ambulating. Subjects who can retain neither device size will be withdrawn from the study.

Study subjects eligible for the study at the end of the baseline period will be given instructions as to ordering the study devices to be shipped to them by Minnesota Medical Technologies. The clinical site will train study subjects in the proper use of devices.

Eligible study subjects will proceed to a up to 4-week fitting period where subjects will evaluate which of two device sizes (10mm or 13mm) is preferred. Subjects who can retain the 10mm device at the screening visit will begin the fitting period with the 10mm device. Subjects who cannot retain the 10 mm but can retain the 13 mm device will begin the fitting period with the 13 mm device. The sequence of events for the fitting period will be as follows:

- 1) Subjects who begin with the 10 mm device will use the device for a minimum of 2 weeks during the fitting period. , Subjects will be asked to complete daily bowel diaries to determine the percent reduction in FI episodes, and subject comfort will be assessed using question #7 on the QUEST questionnaire. If greater than or equal to 75% reduction in FI episodes is observed during this fitting period, the subject will proceed immediately to the treatment period and will continue using the 10mm device for the entire treatment period. If the reduction in FI episodes is less than 75%, and the QUEST score is 1-2 (indicating dissatisfaction with comfort), the subject will proceed immediately to the treatment period and will continue using the 10mm device for the entire treatment period. If the reduction in FI episodes is less than 75%, and the QUEST score is 3-5 (indicating satisfaction with comfort), the participant will use 13 mm devices

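### The n=30 responder test against a historical 30% reads as one test per device size, but size is assigned on fitting response and comfort, so 30% is not a valid null rate for either size group

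*Combined protocol and SAP*

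**What the plan says.** Section 8.2 first justifies numbers for a paired t test and concludes that "a sample size of 30 FI subjects per group (i.e., 10mm and separately 13 mm inserts) is more than sufficient". The next paragraph turns to responders. It begins "In order to test whether the treatment provides an improvement up to 60% response rate (50% response) from an assumed historical rate of 30" per cent, then says that "the exact one-sample binomial test (2-sided) will be used at the 0.05 level" and that "A sample size of n=30 provides 90% power to detect this effect". It does not name the set of 30 subjects. Section 8.1 says that "these endpoints will be assessed for all 60 participants and separately for the 10 mm and 13 mm devices (versus baseline").

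Sections 1.1, 1.2 and 6.1.2 govern who ends up on which size:
- "If greater than or equal to 75% reduction in FI episodes is observed during this fitting period", a subject who started on 10 mm stays on 10 mm.
- "If the reduction in FI episodes is less than 75%, and the QUEST score is 3-5", the subject moves to 13 mm, and stays there if still satisfied with comfort.
- Below 75% with a QUEST comfort score of 1-2, the subject stays on 10 mm. A score of 1-2 on 13 mm returns the subject to 10 mm.
- Subjects who could not retain 10 mm at screening start on 13 mm and stay on it whatever their response.

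Section 8.4.2 excludes fitting diaries from the efficacy evaluation. It does not address their role in forming the size groups.

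**The concern.** A one-sample binomial test compares an observed count with the count expected if each subject responds at the null rate. For a group of 30 that is Binomial(30, 0.30), provided the 30 have not been chosen on something related to response. Here they have. Fitting-period reduction is related to treatment-period response through any persistent subject-level effect, and also because both are measured against the same baseline count. Comfort, the other sorting variable, may be related to response too.

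A size-specific pass or failure could then reflect how the fitting rule sorted subjects rather than what that size does. This is separate from any comparison of 10 mm with 13 mm: each one-sample test has the problem by itself. The stated justification for the primary endpoint is substantial equivalence to a predicate (Section 3), so a size-specific claim could carry weight.

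**Working it through.** **Step 1: the plan's figure.** Inputs from 8.2: p0 = 0.30, p1 = 0.60, n = 30, exact two-sided test at 0.05. The upper rejection limit is 15 or more responders.
- P(X ≥ 15 | 30, 0.30) = 1.7%. One fewer does not qualify: P(X ≥ 14 | 30, 0.30) = 4.0%, above 2.5%.
- P(X ≥ 15 | 30, 0.60) = 90.3%, so the stated 90% reproduces.

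**Step 2: how far the test moves if the group's true rate is not the overall rate.**

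| True rate in the group | P(X ≥ 15 of 30) |
|---|---|
| 0.30 | 1.7% |
| 0.35 | 6.5% |
| 0.40 | 17.5% |
| 0.45 | 35.5% |
| 0.50 | 57% |
| 0.60 | 90.3% |

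**Step 3: what the fitting rule does to the group rates.** This was simulated.
- From the documents: baseline weekly episodes with mean 2.6 and SD 1.066 (8.2), entry at 4 or more episodes in 4 weeks (4.1), and the assignment rule of 6.1.2 with all its branches.
- Model: gamma-Poisson counts. A lognormal subject-level rate ratio persists from a 2-week fitting count to the 4-week treatment count and is the same for both sizes. Response is at least 50% reduction. The overall response rate is fixed at 30% or 60%.
- Assumed, because the documents give no figures: 15% start on 13 mm; 50-90% are comfortable on each size; the SD of the log rate ratio (log-SD) is 0 to 1.0; n is held at 30 per size.

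*Comfort unrelated to response:*

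| Comfortable | Log-SD | Overall 30%: 10 mm rate, upward rejection | Overall 60%: 13 mm rate, power |
|---|---|---|---|
| 50% | 0 | 30.5%, 2% | 58%, 87% |
| 80% | 0.5 | 37%, 9% | 53%, 70% |
| 90% | 1.0 | 51%, 60% | 46%, 40% |

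Over this grid the 10 mm upward rejection is about 2-60% against a nominal 1.7%, and 13 mm power about 40-87% against 90%. A wider grid (95% comfortable; 0% or 20% starting on 13 mm) stretches these to 92% and 19%, so the upper ends reflect the assumptions chosen.

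*Comfort related to response* (log-SD 0.5, overall 30%):
- 80% comfortable in the better-responding half and 60% in the rest: both groups at about 30%, no distortion.
- 90% and 50%: 10 mm at 26%, 13 mm at 34%. The direction reverses, and 10 mm upward rejection falls to about 0.5%.

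**Step 4: the test on all 60.** The split by size does not enter. The upper limit is 26 or more: P(X ≥ 26 | 60, 0.30) = 2.0% and P(X ≥ 26 | 60, 0.60) = 99.7%. One fewer does not qualify: P(X ≥ 25 | 60, 0.30) = 3.6%.

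**The case against.** The strongest objection is textual. The figure of 30 per size closes the paired t-test paragraph, while the binomial paragraph speaks only of the treatment. The separate assessment in 8.1 is against baseline, and the primary endpoint listed there is a percentage reduction, not a responder rate. Section 8.4.2 never mentions the binomial test. So a reader might infer that the protocol explicitly prescribes a test against 30% in each size; it does not. What remains is that a 60-subject trial described as 30 per size, with a responder test sized at 30, offers no other evident set of 30. If another set was meant, the plan still has to name it.

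The second objection concerns direction. A reader might infer that the rule necessarily inflates 10 mm and depletes 13 mm. That would follow if it sorted on response alone, but uncomfortable non-responders stay on or return to 10 mm, and 13 mm starters remain there whatever their response. The documents say nothing on how comfort relates to response, and under plausible links the distortion disappears or reverses. This objection stands in full against any claim of a known direction. It does not rescue Binomial(30, 0.30), which would then be right only if the opposing selections happened to cancel.

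Third, the source and population of the historical 30% are not given. That is true, and it limits the all-60 test as well, but it supplies no reason to think 30% fits a group formed by the fitting rule.

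**Conclusion.** The point holds as a defect in the reference rate for size-specific responder tests, on the natural but inferred reading that 8.2 and 8.1 together plan them. Such tests would not have the error rate or the 90% power that 8.2 implies.

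The magnitude is uncertain. With comfort unrelated to response, 80% comfortable and log-SD 0.5, false passes for 10 mm are about 9% and power for 13 mm is about 70%; the ranges in the working depend on assumed comfort, persistence and the share starting on 13 mm. Neither a false pass for 10 mm nor a failure for 13 mm can be predicted from the documents. The test on all 60 is free of this selection, so the trial's overall responder conclusion is not threatened on this ground. The change should be made, but the point is not fatal to the trial.

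**What to change.** In 8.1 and 8.2, state that the exact binomial test against 30% is a single test on all 60 treated subjects. Replace the n=30 and 90% statement with the n=60 figures: reject upward at 26 or more of 60, upper-tail error 2.0%, power 99.7% at a true 60%, before dropout. Report responder rates by final size with confidence intervals only, labelled as selected on fitting response and comfort, with no test against 30%. Leave the exclusion of fitting diaries in 8.4.2 as it is; a by-size estimate taken from those diaries would conflict with it.

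The cost is wording. No subjects, data or changes to the fitting rule are needed. The sponsor gives up a separate significance claim for each size.
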